## Analysis methods

The number and location of gaps will be presented using summary statistics. Summary statistics are, in this case, frequencies and proportions. Additionally, a contour or density plot may be presented, with higher densities indicating greater numbers of observed reconnections.

### 6.2.4. Objective #4: Ablation lesion sets performed

Summarize ablation lesion sets created during re-ablation procedure.

#### Endpoint Definition

Each lesion set during re-ablation will be classified into one of the following categories:

- Pulmonary vein isolation (PVI)
- LA AF Trigger
- RA AF Trigger
- Superior vena cava trigger
- Inferior vena cava trigger
- Cavoatrial Isthmus (CTI)
- Mitral valve isthmus or line
- Left sided roofline
- Complex fractionated atrial electrogram (CFAE)
- Posterior wall
- AVNRT ablation
- Other

#### Analysis methods

The first re-ablation for each subject will be used for analysis. The number of lesion sets for each subject will be counted. If a subject has multiple PVs ablated, each PV will count as a lesion set towards the subjects total count. The number of lesion sets will be compared between randomization arms using a two-sample t-test.

### 6.2.5. Objective #5: Acute procedural success

Summarize acute procedural success as assessed by the sites.

#### Endpoint Definition:

Definition of success for each lesion set found below

- Pulmonary vein isolation (PVI)
  - Acute failure is defined as inability to isolate the pulmonary vein (minimally assessed for entrance block and, where assessable, exit block). Acute success is defined as the absence of acute failure.
- LA AF Trigger
  - Acute success is defined as elimination of trigger by ablation procedure.
- RA AF Trigger
  - Acute success is defined as elimination of trigger by ablation procedure.
- Superior vena cava trigger

- Acute success is defined as elimination of trigger by ablation procedure.
- Inferior vena cava trigger
- Acute success is defined as elimination of trigger by ablation procedure.
- Cavotricuspid Isthmus (CTI)
- Acute success is defined as bidirectional conduction block at the CTI line
- Mitral valve isthmus ablation
- Acute success is defined as bidirectional conduction block at the mitral isthmus line
- Left atrial roofline
- Acute success is defined as confirmed block at the roof line
- Left atrial posterior wall
- Acute success is defined as confirmed block at the posterior wall
- Complex fractionated atrial electrogram (CFAE)
- Acute success is defined when ablation of electrograms resulted in termination of atrial fibrillation to sinus rhythm or until all complex fractionated regions were completely eliminated
- AVNRT ablation○ Acute success is defined as 1) no AVNRT inducibility; 2) no jump; 3) single echo only.

Other lesion sets may be observed on rare occasions, but acute procedural success will not be assessed for lesion sets not listed above. The denominator of the acute procedural success metric will only include subjects with a 'yes' or a 'no' listed in response to the case report form question as to whether acute procedural success was attained for all lesions.

## Analysis methods

The first re-ablation for each subject will be used for analysis. For subjects receiving only re-isolation of pulmonary veins, acute procedural success is defined as minimally assessed for entrance block, and where assessable, exit block. For subjects receiving additional lesions beyond PVI, acute success is defined as successful PVI plus successful ablations as defined in the endpoint definition for all ablations. Each subject will be classified as an acute procedural success or not. Acute procedural success will be compared between randomization arms using exact methods.

## 6.2.6. Objective #6: Re-ablation procedure times

Summarize re-ablation procedure times.

### Endpoint:

1. *Total procedure time* is defined as time from first venous access to time of last sheath removal.
2. *Left atrial dwell time* is defined as time from transseptal puncture to time of removal of last sheath from the left atrium.
3. *Fluoroscopy time* is defined as total fluoroscopy time used during the procedure.

### Ablation methods

The first re-ablation for each subject will be used for analysis. Procedural times will be compared

between randomization arms with a two-sample t-test. Separate t-tests will be used for each procedure time metric.

## 6.2.7. Objective #7: Hospitalization length of stay

Summarize the length of stay during the hospitalization for re-ablation

### Endpoint Definition

Length of stay is defined as the number of days from admission to discharge.

### Analysis Methods

The first re-ablation for each subject will be used for analysis. Hospital length of stay will be compared between randomization arms with a two-sample t-test. If the distribution of length of stay is skewed non-normal, a non-parametric Wilcoxon test will be utilized.

## 6.2.8. Objective #8: Anti-arrhythmic drug use at discharge

Summarize the anti-arrhythmic drug use at time of discharge from the re-ablation procedure.

### Endpoint Definition

Anti-arrhythmic drug is defined as a Class I or III antiarrhythmic drug prescribed at discharge.

### Analysis Methods

The first re-ablation for each subject will be used for analysis. The percent of subjects discharged from re-ablation on anti-arrhythmic drugs will be compared between randomization arms using exact methods.

## 6.2.9. Objective #9: Adenosine testing

Summarize adenosine testing utilized during re-ablation procedure.

### Endpoint Definition

Use of adenosine testing during re-ablation. Subjects for whom it is unknown whether adenosine testing was performed will not be included in the denominator.

### Analysis Methods

The first re-ablation for each subject will be used for analysis. The percent of subjects with adenosine testing will be compared between randomization arms using binomial exact methods.

## 6.3. Center Pooling

Data from all sites will be combined without regard to center location for the analysis of the study's endpoints. No assessment of site-level heterogeneity is planned.

## 6.4. Handling of Missing, Unused, and Spurious Data and Dropouts

[figure not shown]
It is anticipated that approximately 90% of the eligible subjects will be re-consented (DRF) and have available data from charts with which to perform an abstraction. Of these, some subjects' records will not contain data for one or more endpoints. Also, in some instances, charts from re-consenting subjects may contain complete data, but it will contain values that cannot be used in analysis of one or more objectives (i.e., when the CRF value of 'unknown' is selected instead of 'yes' or 'no'). If, for any of these reasons, 22 or more subjects do not have data for the reconnection of pulmonary veins endpoint (Objective #2) or the acute procedural success endpoint (Objective #5), further analyses relating to missingness of data may be performed.

Demographics of re-do cohorts will be compared. If no major differences in variables collected at baseline in the original Fire and Ice trial are observed between cryo and RF ablation arms, then data will be assumed "Missing Completely At Random" (MCAR) for all objectives, and only complete cases analysis will be performed. However, if differences are present and deemed significant, and <88 subjects have complete data for objectives #2 (reconnection of PV's) and #5 (acute procedural success), then up to two additional sensitivity analyses will be performed.

The sensitivity of between-group differences in reconnected pulmonary veins as a function of possible values in missing subjects will be illustrated graphically in a density plot like the one shown below in **Figure 2**. Regions of the plot that represent the combinations of reconnected PV's per subject observed among missing cryo and RF subjects which produce significant p-values in the between-groups comparison will be highlighted, and summary statistics (mean and SD of # reconnected PV's) for all significant combinations and all non-significant combinations will be displayed by group. The sensitivity of acute procedural success rates to missing data will be assessed for two additional scenarios: the "best case", and the "worst case" scenarios. The best case scenario will be calculated by assuming all subjects from the cryo arm were acute procedural successes compared to none of the RF subjects; the worst case scenario assumes that all cryo arm subjects were acute procedural failures and all RF arm subjects were acute procedural successes. Fisher's exact methods, as described above in **section 6.2.5**, will be used to assess between-therapy arm differences under these two sets of assumptions, and will be presented alongside the complete case scenario.

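### SAP 6.4 infers MCAR from cryo/RF baseline balance, requires no sensitivity analysis when the arms are alike, and words the Objective #5 best and worst cases for all subjects

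*SAP*

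**What the plan says.** SAP section 6.4 expects about 90% of the 110 eligible subjects to consent and have usable charts, with further gaps for single endpoints and for answers recorded as unknown. It then sets out two rules.

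- **Missing count.** If 22 or more subjects lack data for Objective #2 (reconnected veins) or Objective #5 (acute success), "further analyses relating to missingness of data may be performed". These analyses are optional and not described.
- **Arm comparison.** "If no major differences in variables collected at baseline in the original Fire and Ice trial are observed between cryo and RF ablation arms", the assumption follows, in the SAP's words: "MCAR) for all objectives, and only complete cases analysis will be performed". Otherwise, "if differences are present and deemed significant, and <88 subjects have complete data for objectives #2" and #5, up to two sensitivity analyses will be done.

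For Objective #2 the sensitivity analysis shows the result "as a function of possible values in missing subjects". For Objective #5 the aim is similar: "The sensitivity of acute procedural success rates to missing data will be assessed". But the best case is defined by "assuming all subjects from the cryo arm were acute procedural successes compared to none of the RF subjects", and the worst case is the reverse.

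SAP section 6.2.5 settles the complete-case set for Objective #5: "The denominator of the acute procedural success metric will only include subjects with" a yes or no answer on the case report form.

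**The concern.** MCAR is a statement about subjects with an endpoint value compared with subjects without one. The SAP compares cryo with RF instead. Two arms can be perfectly balanced while the subjects with missing charts differ sharply from the rest, and two arms can be unbalanced with data missing purely by chance. The check therefore cannot support the assumption drawn from it.

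The same check also gates the only defined sensitivity analyses. Objective #5 is tested between arms at the 0.05 level, and unknown answers leave its denominator, so who is missing affects the reported rates. The disposition figure in SAP section 6.1.1 reports how many subjects lack data, not how they differ. A complete-case comparison could thus be reported under an unexamined assumption, with no bound on what the missing subjects could change.

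The Objective #5 scenarios are a separate matter. Programmed as written, they return the same answer for any data and so measure no sensitivity to missing data.

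**Working it through.** **1. The plan's thresholds.** 110 − 22 = 88 and 22/110 = 20%, so the two cut-offs come from the same figure. They do not match exactly: 22 or more missing means 88 or fewer complete, while fewer than 88 complete means 23 or more missing. Exactly 22 missing meets the first rule and not the second. The link between Objectives #2 and #5 also changes from *or* to *and*.

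| Missing | Arms alike at baseline | Arms differ |
|---|---|---|
| 0–21 | nothing | nothing |
| 22 | optional, undefined | optional, undefined |
| 23 or more | optional, undefined | up to two named analyses |

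**2. Can arm balance reveal the missingness mechanism?** Simulation with assumed inputs: 44 cryo and 66 RF subjects, four veins each, reconnection probability 0.475 in both arms (no true difference), one baseline covariate balanced between arms, 6,000 runs per scenario.

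| Missingness | Mean missing | Arm check passes | Missing-versus-observed check flags | Complete-case t-test rejects |
|---|---|---|---|---|
| MCAR (0.22 throughout) | 24.2 | 95% | 5% | 5.6% |
| Depends on covariate (0.40 vs 0.04) | 24.3 | 95% | 98% | 5.1% |
| Depends on outcome, opposite by arm (0.35 vs 0.08) | 22.8 | 95% | 5% | 23% |

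The arm check passes equally often in all three. In the last row the complete-case RF − cryo difference averages +0.27 veins when the truth is 0. The missing-versus-observed check finds covariate-dependent missingness but not purely outcome-dependent missingness, so no baseline test should decide whether a sensitivity analysis is run.

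**3. What missing subjects could do to Objective #5.** The documents do not give the number of subjects by arm. The protocol's background section gives repeat-ablation rates of 11.8% of 378 and 17.6% of 384, i.e. 44.6 and 67.6; scaled to 110, the cryo share is 110 × 44.6/(44.6 + 67.6) ≈ 44, leaving 66 RF. The 49/70 split of procedures gives 110 × 49/119 ≈ 45. I assume 44/66 and use the two-sided Fisher exact test. Best = missing cryo succeed and missing RF fail; worst = the reverse; observed outcomes are kept.

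| Scenario | Observed | Best | Worst |
|---|---|---|---|
| 21 missing (8 cryo, 13 RF) | 32/36 vs 48/53, p = 1.0 | 40/44 vs 48/66, p = 0.027 | 32/44 vs 61/66, p = 0.007 |
| 11 missing (4, 7), about 95% success | 38/40 vs 56/59, p = 1.0 | 42/44 vs 56/66, p = 0.119 | 38/44 vs 63/66, p = 0.152 |
| 11 missing (4, 7), about 85% success | 34/40 vs 50/59, p = 1.0 | 38/44 vs 50/66, p = 0.226 | 34/44 vs 57/66, p = 0.303 |
| 11 missing (4, 7), 100% success | 40/40 vs 59/59, p = 1.0 | 44/44 vs 59/66, p = 0.040 | 40/44 vs 66/66, p = 0.024 |
| 99 consenters only (40/59), 4 and 6 missing | 32/36 vs 48/53, p = 1.0 | 36/40 vs 48/59, p = 0.270 | 32/40 vs 54/59, p = 0.131 |

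With 21 missing, divided between the arms in proportion to size, splits from 42/68 to 48/62 and observed success from 80% to 95% give best-case p from 0.006 to 0.051 and worst-case p from 0.002 to 0.042.

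**4. The Objective #5 scenarios as worded.** With 40 cryo and 59 RF subjects: 40/40 vs 0/59, p = 1.2 × 10⁻²⁸, and the same p in reverse. No observed outcome enters the calculation.

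**The case against.** - **The Objective #5 wording is a slip.** The sentence before it speaks of missing data, the results are to stand beside the complete-case result, and the Objective #2 analysis is limited to missing subjects. I agree that missing subjects were probably meant, and the extreme p-value carries no weight beyond showing that the text cannot be programmed as it stands.
- **The 21-missing case is pessimistic.** It is nearly twice the expected shortfall of about 11, and it imputes across all 110, whereas the full analysis set in SAP section 6.1.3 is consenting subjects only. This stands as a limit on size. At 11 missing the bounds usually stay above 0.05, except near 100% success, and for consenters only they are 0.27 and 0.13. However, section 6.4 itself expects endpoint gaps and unknown answers beyond the 10%.
- **A 20% cut-off is a design choice, and the one-subject mismatch rarely matters.** True, but the arm-balance condition removes the requirement at any level of missingness.
- **A within-arm comparison of subjects with and without data is weak.** Power for a 0.5 SD difference is roughly 15% to 36% at these numbers, and a null result could again be read as MCAR. This stands, and is why the sensitivity analyses should not depend on it.
- **The study is mainly descriptive, its between-arm inference is acknowledged as limited, and extra analyses are allowed.** This lowers the severity. It does not make the rule correct: the acknowledged limit concerns selection into re-ablation, and the SAP itself singled out Objectives #2 and #5 for missing-data checks.

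**Conclusion.** The concern holds and should be fixed. The MCAR rule rests on a comparison that carries no information about missingness. With balanced arms the plan requires no sensitivity analysis at any amount of missing data. The Objective #5 scenarios, read literally, do not depend on the data.

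The practical effect depends on how much is missing. At 21 missing, a null-looking result could be significant in either direction under missing-only bounds; at the planned availability it usually could not. These are extreme bounds, not predictions, and they rest on the assumed arm split, missing counts and success rates. The faults in the rule and in the wording rest on none of these assumptions.

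**What to change.** Amend SAP section 6.4:

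1. Delete the step from arm balance to MCAR. Compare baseline variables from the FIRE AND ICE Trial between subjects with and without each endpoint, within arm, among consenting subjects. Report this as description, not as a test that licenses MCAR. Include non-consenters only where consent and data-protection rules allow (protocol section 13.1).
2. Run the Objective #2 and #5 sensitivity analyses regardless of arm differences: either whenever any subject lacks the endpoint, or at one aligned trigger (22 or more missing, equal to 88 or fewer complete) applied to each objective separately. State whether non-consenters count as missing. The 110 − 22 arithmetic implies that they do for the trigger, but the full analysis set excludes them.
3. Restrict the Objective #5 best and worst cases to subjects with missing success status, keeping observed outcomes.

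The cost is rewording and a few extra tables. No new data are needed if the work is limited to consenting subjects; describing non-consenters would need a check against local rules.

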13.1. General Considerations

A total of 119 repeat ablations were reported in 110 subjects in the FIRE AND ICE Trial. The primary analysis cohort for this CIP will be subjects that provide informed consent for a retrospective data collection (as required). Of the 110 subjects with re-ablations during the FIRE AND ICE Trial, only those that consent for retrospective data collection will be included in analyses (as required by local law / EC).

The Statistical Analysis Plan (SAP) will be created prior to data analysis and include a comprehensive description of the statistical methods to be included in study reports. Any change to the data analysis methods described in the CIP will require an amendment only if it changes a principal feature of the CIP. Any other change to the data analysis methods described in the CIP, and the justification for making the change, will be described in the clinical study report. Medtronic employees or their designated representatives will perform all statistical analyses.

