## 6.1.3. Analysis Sets

The full analysis set consists of all subjects who agreed to the additional data collection. The full analysis set will be used for all study objectives.

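### The best- and worst-case analyses of acute procedural success, as worded, overwrite every subject's outcome, so both results are fixed in advance and say nothing about missing data

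*SAP*

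**What the plan says.** SAP 6.4 states the aim: "The sensitivity of acute procedural success rates to missing data will be assessed for two additional scenarios". It then defines them.

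- Best case: "assuming all subjects from the cryo arm were acute procedural successes compared to none of the RF subjects".
- Worst case: "the worst case scenario assumes that all cryo arm subjects were acute procedural failures and all RF arm subjects were acute procedural successes".

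Each scenario is tested between arms with Fisher's exact method, by reference to SAP 6.2.5, and shown next to the complete-case result. The companion analysis for reconnected pulmonary veins (Objective #2), in the same paragraph, is worded differently: it varies the vein counts "observed among missing cryo and RF subjects which produce significant p-values".

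Three other places bear on who is counted.

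- SAP 6.2.5: "The denominator of the acute procedural success metric will only include subjects with a" definite yes or no on the case report form.
- SAP 6.1.3: "The full analysis set consists of all subjects who agreed to the additional data collection", and this set serves all objectives.
- Protocol 13.1: "only those that consent for retrospective data collection will be included in analyses".

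The scenarios are conditional. They run "if differences are present and deemed significant" (this refers to baseline variables compared between arms) and fewer than 88 subjects have complete data for Objectives #2 and #5.

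**The concern.** A best-case/worst-case analysis keeps what was observed and puts the extreme values only where the outcome is unknown. The SAP's definitions cover whole arms. The restriction to missing subjects is written out for Objective #2 and absent for Objective #5, and nothing elsewhere in the SAP or protocol supplies it.

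Taken literally, the rule discards all observed outcomes and compares two invented tables, one in each direction. Both will be significant, so the pair cannot show whether the complete-case conclusion is robust.

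The denominator is a second gap. SAP 6.4 does not state one, and the only denominator given for this endpoint, in SAP 6.2.5, leaves out the very subjects whose outcomes would need to be filled in.

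When the trigger is met, these are the only sensitivity analyses planned for Objective #5. If the problem is noticed only then, the rule and its denominator would be chosen after database freeze, when the arm comparison can already be seen.

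**Working it through.** The documents give no numerical result for these scenarios, so there is no figure to reproduce. The check compares the literal rule with the missing-only rule.

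**Inputs**

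- Eligible subjects: 110 (protocol 13.1). Subjects per arm are not given; protocol 4.1 gives 49 and 70 re-ablation procedures.
- Assumed split, from the repeat-ablation percentages in protocol 4.1: 378 × 0.118 = 44.6 and 384 × 0.176 = 67.6. Scaled to 110 these are 43.7 and 66.3, taken as 44 cryo and 66 RF.
- About 90% re-consent with data (SAP 6.4): 40 cryo and 59 RF, total 99.
- Trigger: fewer than 88 complete, so 87 complete is used (35 cryo, 52 RF). Missing: 99 − 87 = 12 among consenters (5/7), or 110 − 87 = 23 among all eligible (9/14).
- Observed success rates are assumptions. Fisher tests are two-sided; the SAP sets alpha at 0.05 but not the sidedness.

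**Literal rule**

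With n₁ cryo and n₂ RF subjects, the tables are n₁/n₁ vs 0/n₂ and 0/n₁ vs n₂/n₂. The Fisher p-value is 1/C(n₁+n₂, n₁), doubled when the arms are equal. It contains no observed outcome and is the same in both scenarios.

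| Cryo / RF | p, both scenarios |
|---|---|
| 44 / 66 | 9e-32 |
| 40 / 59 | 1e-28 |
| 35 / 52 (yes/no answers only) | 4e-25 |
| 35 / 75 | 2e-29 |
| 55 / 55 | 2e-32 |
| 10 / 10 | 1e-5 |
| 4 / 4 | 0.029 |

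The arm split is therefore immaterial to the conclusion.

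**Missing-only rule**

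Let s be the observed successes and m the number missing in each arm.

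- Best case: (s₁+m₁)/n₁ vs s₂/n₂.
- Worst case: s₁/n₁ vs (s₂+m₂)/n₂.

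| Denominator (missing) | Observed | Complete-case p | Best case | Worst case |
|---|---|---|---|---|
| 40/59 (5/7) | 32/35 vs 47/52 | 1.0 | 37/40 vs 47/59, p = 0.094 | 32/40 vs 54/59, p = 0.131 |
| 40/59 (5/7) | 28/35 vs 49/52 | 0.082 | 33/40 vs 49/59, p = 1.0 | 28/40 vs 56/59, p = 0.0011 |
| 40/59 (5/7) | 35/35 vs 52/52 | 1.0 | 40/40 vs 52/59, p = 0.039 | 35/40 vs 59/59, p = 0.0092 |
| 44/66 (9/14) | 33/35 vs 49/52 | 1.0 | 42/44 vs 49/66, p = 0.0041 | 33/44 vs 63/66, p = 0.0026 |
| 44/66 (9/14) | 28/35 vs 49/52 | 0.082 | 37/44 vs 49/66, p = 0.25 | 28/44 vs 63/66, p = 0.00004 |

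With 40/59, missing splits of 4/8, 5/7 and 6/6, and equal observed success of about 80% to 95%, the best case gives p = 0.07 to 0.24 and the worst case p = 0.03 to 0.28. The missing-only rule can fall either side of 0.05.

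**Does the denominator matter?**

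Take the same complete cases, 32/35 vs 47/52. On 40/59 the p-values are 0.094 and 0.131, as above. On 44/66 the best case is 41/44 vs 47/66, p = 0.0065, and the worst case is 32/44 vs 61/66, p = 0.0070. The reading changes with the denominator alone.

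**The case against.** The strongest reply is that the intent is plain. The section concerns missing data, the lead-in says so, the companion analysis imputes only missing subjects, and placing the result beside the complete cases makes sense only if observed outcomes are kept. A second statistician reviews the code (SAP 8), and a table of 100% vs 0% would be hard to overlook. All of this is fair, and missing-only imputation was very probably meant. But the SAP is the specification that the program is reviewed against, and inferring the intent still leaves the denominator open.

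It can also be said that SAP 6.4 cites 6.2.5 for the test and not for its denominator. That is a reasonable reading; on it the denominator is simply unstated, which still needs repair.

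A further point concerns the full analysis set as the remedy. The SAP's two thresholds, 22 without data and 88 complete, add to 110, so the trigger appears to count subjects who did not consent. Using consenters only means that such subjects help to trigger the analysis but are never imputed. The mismatch is real and should be acknowledged, but SAP 6.1.3 and protocol 13.1 both confine analysis to consenting subjects, so the choice is sound.

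Finally, the reach is narrow: the trigger is conditional, SAP 7 calls the objectives generally descriptive and singles out Objective #2, and SAP 6.8 requires deviations to be justified in the report. This limits the harm. It does not make the two scenarios informative.

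**Conclusion.** The concern holds. As worded, the success rates, the direction and the significance of both scenarios are settled before any outcome is known; only the exact p-value moves, and only with the arm sizes. This rests on the text and on no assumption about the data, since even four subjects per arm would give p = 0.029. The missing-only illustrations do rest on assumed arm sizes, missing counts and success rates; they show that the corrected analysis would be informative, not what it would find.

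The primary Objective #5 comparison is unaffected. The change should be made, as a cheap repair to a conditional sensitivity analysis.

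**What to change.** Replace the two definitions in SAP 6.4 with wording such as:

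> Best case: cryo-arm subjects with a missing or unknown acute procedural success outcome are counted as successes, and RF-arm subjects with a missing or unknown outcome as failures. Worst case: the reverse. Observed outcomes are retained. The denominator is the full analysis set (SAP 6.1.3), not the yes/no-only denominator of SAP 6.2.5.

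The sponsor should confirm the denominator and state whether non-consenting subjects count towards the trigger of fewer than 88 complete cases. The cost is two or three sentences, with no new data, and the change should be made before database freeze.
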